### **3.0 STUDY OBJECTIVES**

#### **3.1 Primary Objective**

The primary objective of this study is to determine the efficacy of PCI-32765, both as a single agent and in combination with dexamethasone, in subjects with relapsed or relapsed and refractory MM as measured by clinical benefit response rate (CBR), defined as the proportion of subjects who achieved stringent complete response (sCR), complete response (CR), very good partial response (VGPR), partial response (PR), or minimal response (MR) as assessed by the modified International Myeloma Working Group (IMWG) response criteria.

#### **3.2 Secondary Objectives**

Secondary objectives are to evaluate the efficacy of PCI-32765 in this population as assessed by the following:

- Duration of clinical benefit (DCB)
- Objective response rate (ORR)
- Duration of objective response (DOR)
- Safety (assessed by reporting of SAEs, AEs, and treatment-related discontinuations)
- Pharmacokinetics (assessed by sampling and testing for drug and metabolite levels at designated time points)

#### **3.3 Exploratory Objectives**

- Progression-free survival (PFS)
- Time to progression (TTP)
- Overall survival (OS)

#### **3.4 Exploratory Analyses**

- Prognostic and predictive biomarkers and genetics relative to treatment outcomes.

### **4.0 STUDY DESIGN**

#### **4.1 Description of Study**

This is a Phase 2, open-label, nonrandomized, multi-cohort, multicenter Simon 2-stage study designed to assess the safety and efficacy of PCI-32765 in subjects with relapsed or relapsed and refractory MM.

Treatment of PCI-32765 420 mg once daily in the original protocol (hereafter referred to as Cohort 1) was designed to detect a meaningful signal of activity while minimizing risk of continuing enrollment under null conditions. Amendment 1 was designed to further explore the

optimal regimen by increasing doses of PCI-32765 and/or by routine combination with low dose dexamethasone.

Cohorts 1 and 3 test activity of PCI-32765 monotherapy; Cohorts 2 and 4 test PCI-32765 in combination with LD dexamethasone.

### Stage 1:

- Up to eighteen (18) subjects will be enrolled to each Cohort 2, 3 and 4, for a maximum total of 54 subjects.
- Stage 1 enrollment to Cohorts 3 and 4 may begin concurrently after Cohort 2 Stage 1 enrollment is complete. If there is concurrent enrollment, Sponsor will implement centralized assignments into cohorts.

### Stage 2:

- If  $\geq 3$  CBRs are observed within Cohorts 2, 3, or 4 in Stage 1, the cohort(s) may be selected for expansion for up to a total enrollment of 43 subjects or until observing  $\geq 8$  CBRs, whichever occurs earlier.
- If there is concurrent Stage 2 enrollment to more than 1 cohort at any given time, Sponsor will implement centralized assignments into cohorts.

Sponsor maintains the prerogative to select regimen, which gives optimal efficacy and safety results at interim analysis for further development while suspend other cohorts at any time.

The expected total enrollment is between 67 (minimal) and 164 subjects. Dosages and regimens by cohort are summarized in Table 1.

**Table 1: Treatment Cohorts and Planned Enrollment**

Cohort	PCI-32765 (mg/day)	Dexamethasone	Planned First Stage Enrollment	CBR Criteria for First Stage	Total Enrollment (First and Second Stages)
1	420	Upon PD, 40 mg once weekly is allowed †	11*	$\geq 2$	35
2	560	40 mg once weekly	18	$\geq 3$	43
3	840	Upon PD, 40 mg once weekly is allowed †	18	$\geq 3$	43
4	840	40 mg once weekly	18**	$\geq 3$	43

\* n=11 planned for Cohort 1 First Stage, n=13 were enrolled. The decision for second stage expansion will be based on the number of CBR in the first 11 subjects.

[figure not shown]
\*\* n=18 planned for Cohort 4 First Stage, n=20 were enrolled. The decision for second stage expansion will be based on the number of CBR in the first 18 subjects.

† For Cohorts 1 and 3 subjects who have confirmed PD, and who are clinically stable, without significant worsening of symptoms or hematologic status (ie, meet all entry criteria for the study in regard to symptoms and hematology), will be eligible to receive dexamethasone 40 mg orally once per week in addition to continued treatment with PCI-32765, at the discretion of the investigator.

Subjects are allowed to continue study drug as long as the subject is clinically stable (SD or better) and the subject is not experiencing any unacceptable toxicity. Subjects in the monotherapy cohorts (1 and 3) who have PD confirmed as required by definition in [Appendix 5](#), and without significant worsening of symptoms or hematologic status (ie, meet all entry criteria for the study in regard to symptoms and hematology), will be eligible to receive dexamethasone 40 mg p.o. once per week in addition to continued treatment with PCI-32765, at the discretion of the investigator. Otherwise, subjects having PD will be removed from study.

A flowchart summary of the PCYC-1111-CA study design is provided in Section 4.1.1. For a complete description of procedures refer to Study Procedures ([Section 7.0](#)).

#### 4.1.1 Study Summary Flow Diagram

- In Stage 1 enrollment, up to 18 subjects will be enrolled to each Cohort 2, 3 and 4.
- Stage 1 enrollment to Cohorts 3 and 4 may begin concurrently after Cohort 2 Stage 1 enrollment is complete.
- If there is concurrent enrollment to more than 1 Cohort (Stage 1 or 2), Sponsor will implement centralized treatment assignments.
- Sponsor maintains the prerogative to select regimen which gives optimal efficacy and safety results at interim analysis for further development while suspend other cohorts at any time.

## 4.2 Endpoints

### 4.2.1 Primary Endpoint

The primary endpoint of the study is the CBR, defined as the proportion of subjects achieving an MR or better as assessed by investigator per modified IMWG criteria ([Appendix 5](#)).

### 4.2.2 Secondary Endpoints

The secondary endpoints for this study are as follows:

Safety:

- Safety parameters including the incidences and types of clinical adverse events, laboratory variables, and vital signs measurements

Efficacy:

- Duration of clinical benefit (DCB)
- Objective response rate (ORR)
- Duration of objective response (DOR)

Pharmacokinetics:

- Plasma PK of PCI-32765 and metabolite PCI-45227

**4.2.3 Exploratory Endpoint**

- Progression-free survival (PFS)
- Time to progression (TTP)
- Overall survival (OS)

**4.3 Correlative Assessments on Bone Marrow Aspirate**

Exploratory analysis of bone marrow aspirate samples are planned to be performed on all subjects in Cohort 4 expansion to investigate possible mechanisms of treatment sensitivity and resistance.

Bone marrow aspirate specimens will be collected prior to start of dosing, if CR is suspected and at progression. The sample obtained at progression may be at any time from when progression occurs, and the patient is taken off treatment, up to the start of a different treatment.

The bone marrow aspirate will be analyzed centrally using fluorescence in-situ hybridization (FISH) and the analysis may include, but is not limited to the following probes: t(11;14), t(4;14), t(14;16), del 13q and del 17p. The remaining bone marrow aspirate specimen will undergo flow cytometry analysis and may be processed by CD138+ enrichment. If sufficient sample is available it will be used for the following assessments: Whole Exome Sequencing (WES), RNA sequencing (RNASeq), and gene alteration analysis.

Instructions for collection, processing, and shipping will be in the Laboratory Manual accompanying this protocol.

**4.4 Statement of Compliance**

This study will be conducted in compliance with this protocol, principles of International Conference on Harmonization (ICH) GCP, Declaration of Helsinki, and all applicable national and local regulations governing clinical studies.

## 5.0 SELECTION OF SUBJECTS

### 5.1 Major Inclusion Criteria

#### *Disease Related*

1. Diagnosis of symptomatic MM (as defined by modified IMWG criteria, refer to [Appendix 3](#)) with measurable disease, defined here as having at least one of the following:
  - Serum monoclonal protein (M-protein)  $\geq 0.5$  g/dL as determined by serum protein electrophoresis (SPEP)
  - Urine protein electrophoresis (UPEP)  $\geq 200$  mg/24 hrs
  - Serum free light chain (FLC) assay: involved FLC level  $\geq 10$  mg/dL ( $\geq 100$  mg/L) provided serum FLC ratio is abnormal
2. Relapsed or relapsed and refractory MM after receiving at least 2, but no more than 5, previous lines of therapy, 1 of which must be an immunomodulator (eg, Revlimid®, thalidomide).
  - Refractory myeloma (to most recent treatment) is defined as disease that is nonresponsive while on treatment or progressive disease within 60 days after the completion of preceding treatment. Nonresponsive disease is defined as either failure to achieve minimal response or development of progressive disease while on therapy.
    - Subjects considered refractory to their most recent line of therapy will be ineligible if the most recent line included an immunomodulatory drug and proteasome inhibitor.
  - Relapsed myeloma is defined as the occurrence of any of the following after most recent treatment:
    - $> 25\%$  increase in M-protein from the lowest value obtained while on treatment (absolute increase must be  $\geq 0.5$  g/dL by SPEP,  $\geq 200$  mg/24h by UPEP or  $>10$  mg/dL by serum FLC); or
    - increase in the size and number of lytic bone lesions recognized on radiographs (compression fractures per se do not constitute a relapse).

#### *Demographic*

3. Men and women  $\geq 18$  years of age.
4. Eastern Cooperative Oncology Group (ECOG) performance status of  $\leq 1$
5. Life expectancy of  $\geq 12$  weeks.

#### *Ethical/Other*

6. Ability to understand and willingness to sign a written informed consent form (ICF).

7. Ability to adhere with the study visit schedule and other protocol procedures.

## 5.2 Major Exclusion Criteria

### *Disease Related*

41. Subjects must not have primary refractory disease defined as disease that is nonresponsive in subjects who have never achieved a MR or better with any therapy.
9. Polyneuropathy, organomegaly, endocrinopathy, M-protein, and skin changes (POEMS) syndrome, osteosclerotic myeloma, or Crow-Fukase syndrome.
10. Plasma cell leukemia.
11. Primary amyloidosis.
12. Must not have had any cancer-directed systemic therapy including chemotherapy, immunomodulator or proteasome inhibitor within 3 weeks OR corticosteroid (> 10 mg/day prednisone equivalent systemic exposure) within 2 weeks, of the first dose of study drug.
13. Radiotherapy within 21 days of Cycle 1 Day 1. However, if the radiation portal was localized to single lesion or fracture site and covered by  $\leq 5\%$  of the bone marrow reserve (by investigator estimate), the subject may be enrolled irrespective of the end date of radiotherapy.
14. Treatment with an anticancer antibody within 6 weeks of first dose of study drug.
15. Concurrent enrollment in another therapeutic investigational clinical study, or treatment with an investigational agent within 3 weeks prior to beginning study drug or within 5 drug half-lives.
16. Prior treatment with PCI-32765 or any other protein kinase inhibitory drug or drug targeting the BCR signal transduction pathway.

### *Laboratory*

17. Absolute neutrophil count (ANC) < 750 cells/ $\mu\text{L}$  ( $0.75 \times 10^9/\text{L}$ ) independent of growth factor support.
18. Platelet count < 50,000 cells/ $\mu\text{L}$  ( $50 \times 10^9/\text{L}$ ) independent of transfusion support.
19. Serum aspartate transaminase (AST) or alanine transaminase (ALT)  $\geq 3.0$  x upper limit of normal (ULN).
20. Total bilirubin > 2.5 x ULN, unless due to Gilbert's syndrome.
21. Creatinine > 2.5 mg/dL.

*Concurrent Conditions*

23. Major surgery within 2 weeks of the first dose of study drug.
24. Concomitant therapy with denosumab (bisphosphonate is allowed).
26. Currently active, clinically significant cardiovascular disease such as uncontrolled or symptomatic arrhythmias, congestive heart failure, or myocardial infarction within 6 months of screening, any Class 3 or 4 cardiac disease as defined by the New York Heart Association Functional Classification, or evidence of QT prolongation (QTc > 470 msec).
27. Unable to swallow capsules or disease significantly affecting gastrointestinal function, such as malabsorption syndrome, resection of the stomach or small bowel, or complete bowel obstruction.
28. History of prior malignancy, with the exception of the following:
  - a. Malignancy treated with curative intent and with no known active disease present for more than 3 years prior to screening and felt to be at low risk for recurrence by treating physician;
  - b. Adequately treated non-melanoma skin cancer or lentigo maligna without current evidence of disease; or
  - c. Adequately treated breast or cervical carcinoma in situ without current evidence of disease.
29. Peripheral neuropathy Grade  $\geq 2$  on clinical examination within 14 days prior to enrollment.
30. Uncontrolled diabetes mellitus.
31. Currently active systemic fungal, bacterial, viral, or other infection not controlled (defined as exhibiting ongoing signs/symptoms related to the infection and without improvement, despite appropriate antibiotics or other treatment).
32. Use of antibiotics for treatment of infection within 7 days prior to first dose of study drug.
33. Known history of infection with human immunodeficiency virus (HIV) or history of active infection with hepatitis C virus (HCV) or hepatitis B virus (HBV) or any uncontrolled active systemic infection.
34. History of stroke or intracranial hemorrhage within 6 months prior to the first dose of study drug.
39. Requires anticoagulation with warfarin or a vitamin K antagonist (eg, phenprocoumon).
40. Requires treatment with strong CYP3A4/5 inhibitors (see [Appendix 2](#)).

*Ethical/Other*

35. Subject is pregnant or breastfeeding.
36. Will not agree to use highly effective contraception (eg, condoms, implants, injectables, combined oral contraceptives, some intrauterine devices [IUDs], sexual abstinence, or sterilized partner) during the study and for 30 days after the last dose of study drug. (Note: applies to women of childbearing potential or men with female partners of childbearing potential only.)
37. Any other life-threatening illness, medical condition or organ system dysfunction that, in the investigator's opinion, could compromise the subject's safety, or put the study outcomes at undue risk.
38. Any medical or psychiatric condition that, in opinion of investigator, could interfere with the subject's ability to give informed consent, compliance, or treatment.

**6.0 TREATMENT OF SUBJECTS****6.1 Randomization and Blinding**

This is an open-label study. Subjects will not be blinded to study drug nor will they be randomly assigned to a treatment group. Enrolled subjects will receive open-label PCI-32765 capsules.

**6.2 Formulation, Packaging, and Storage**

PCI-32765 is provided in hard gelatin capsules containing 140 mg of PCI-32765. The capsules are packaged in opaque high-density polyethylene plastic bottles with labels bearing the appropriate label text as required by governing regulatory agencies. The drug product is manufactured for Pharmacyclics LLC, by a contract manufacturer. All formulation excipients are compendial and are commonly used in oral formulations.

The recommended storage condition for PCI-32765 capsules is 15 to 25°C; excursions permitted to 30°C. Refer to the IB for additional information regarding the drug product to be used in this study.

If a drug shipment arrives damaged, or if there are any other drug complaints, please refer to the pharmacy study binder for further instructions.

**6.3 Dosage and Administration****6.3.1 PCI-32765**

PCI-32765 140-mg capsules are intended to be administered orally once daily with 8 ounces (approximately 240 mL) of water (avoid grapefruit or Seville orange juice due to CYP450 3A4/5 inhibition). The capsules should be swallowed intact and subjects should not attempt to open

capsules or dissolve them in water. Subjects should refrain from taking the study drug on the morning of study visits designated for PK sampling until seen at the site (see [Section 7.1.2](#)). One cycle of treatment is once-daily administration of PCI-32765 for 28 days.

Dosages are as follows:

Cohort	PCI-32765 (mg/day)	Dexamethasone
1	420 (3 capsules)	Upon PD, 40 mg once weekly is allowed
2	560 (4 capsules)	40 mg once weekly
3	840 (6 capsules)	Upon PD, 40 mg once weekly is allowed
4	840 (6 capsules)	40 mg once weekly

Subjects will continue on study drug until PD, withdrawal of consent, or until discontinuation of study drug due to an AE. Subjects may continue study drug as long as the subject is deriving clinical benefit (SD or better) and the subject is not experiencing any unacceptable toxicity.

PCI-32765 capsules should be taken at approximately the same time each day. If a dose is missed, it can be taken as soon as possible on the same day with a return to the normal schedule the following day. The missed dose will not be made up and must be returned to the site at the next scheduled visit.

A subject diary will be used to aid with study drug administration compliance.

Only enough PCI-32765 capsules to supply subject until the next study visit should be dispensed with the exception of Cycle 1 where enough PCI-32765 capsules for the entire cycle can be dispensed. Unused PCI-32765 capsules dispensed during previous visits must be returned and drug accountability records ([Section 10.8](#)) updated according to the schedule in [Appendix 4](#).

Returned capsules must not be re-dispensed to the same subject or to another subject.

Investigators are prohibited from supplying PCI-32765 capsules to any subject not properly enrolled in this study or to any physician or scientist except those designated as subinvestigators on Form FDA 1572. The investigator must ensure that subjects receive PCI-32765 capsules only from personnel who fully understand the procedures for administering the study drug.

### 6.3.2 Dexamethasone

Subjects receiving dexamethasone will receive 40 mg orally once per week. Dexamethasone may be taken as either a single dose in the morning or as divided doses over the course of the day.

### **6.3.3 Combination of PCI-32765 and Dexamethasone Dosing**

#### **6.3.3.1 For Subjects with PD (Cohorts 1 and 3)**

At the discretion of the investigator and after Cycle 1, subjects in Cohorts 1 and 3 who have PD and who are clinically stable, without significant worsening of symptoms or hematologic status (ie, meet all entry criteria for the study in regard to symptoms and hematology), will be eligible to receive dexamethasone 40 mg orally once per week in addition to continued treatment with PCI-32765. PD should be confirmed or have repeat laboratory samples collected prior to addition of dexamethasone. Dexamethasone administration may commence at any time during a PCI-32765 cycle. Blood samples for PK should be obtained during the initial cycle with added dexamethasone (Cohort 1 and 3 only), according to [Section 7.1.2](#).

#### **6.3.3.2 Concurrent Dosing of PCI-32765/Dexamethasone Combination (Cohorts 2 and 4)**

PCI-32765 will be administered orally once daily at dosages of 560 mg (Cohort 2) and 840 mg (Cohort 4). Dexamethasone 40 mg will be administered orally once weekly, starting Day 4 of Cycle 1. The rationale for this timing is to 1) prevent toxicity from dexamethasone confounding safety and tolerability as might occur if administered concurrently on Day 1, and 2) to allow intra-subject assessment of impact of dexamethasone on PCI-32765 PK.

#### **6.3.3.3 Concurrent Dosing of PCI-32765/Dexamethasone Combination (Cohort 4 expansion)**

PCI-32765 will be administered orally once daily at a dose of 840 mg (6 x 140 mg capsules). Dexamethasone 40 mg will be administered orally once weekly, starting Day 8 of Cycle 1, following completion of the 7 hour postdose PK sample collection.

### **6.4 Early Cellular Mobilization**

Administration of PCI-32765 to subjects with other lymphoproliferative diseases has been associated with mobilization of tumor cells from tissue to peripheral blood. This effect begins in some cases within hours of the first administration and has been maximal within weeks. It has been often accompanied by rapid symptomatic improvement. It is therefore possible that increased MM cells will appear in the blood samples collected early on in the treatment of subjects during this study. If such a phenomenon occurs, continued observation or treatment should be discussed with the medical monitor. Note: an increase in the presence of circulating plasma cells in peripheral blood in the absence of other indicators of active disease is not an indicator of PD.

### **6.5 Criteria for Holding or Adjusting Study Drug Dose**

#### **6.5.1 Criteria for Holding PCI-32765**

Dosing will be held for any of the following conditions:

- Grade 4 ANC (< 500/ $\mu$ L) for > 7 days (neutrophil growth factors are permitted).
- Grade 3 Platelets (< 50,000/ $\mu$ L) in the presence of clinically significant bleeding
- Grade 4 Platelets (< 25,000/ $\mu$ L)
- Grade 3 or 4 nausea, vomiting, or diarrhea (if persistent despite optimal anti-emetic and/or antidiarrheal therapy).

Any other related grade 4 toxicities and any unmanageable nonhematologic Grade 3 toxicities.

**Table 2: Drug Discontinuation Actions for Subjects on PCI-32765**

Action to be taken - Hematologic Adverse Events	

 
• May resume therapy once ANC <math>\geq</math>750, follow dose modification guidelines below after first occurrence
 
• May resume therapy once platelets >25,000 and no evidence of clinically significant bleeding, follow dose modification guidelines below after first occurrence
 
	
Occurrence	Action to be Taken - Non-hematologic Adverse Events
First	Withhold study drug until recovery to Grade $\leq$ 1 or baseline; may restart at original dose level
Second	Withhold study drug until recovery to Grade $\leq$ 1 or baseline; may restart at 1 dose level lower (ie, Phase 1: 420 mg/day for 560 mg /day cohort; or 700 mg/day for 840 mg/day cohort or Phase 2b: reduce daily dose by 1 capsule/day)
Third	Withhold study drug until recovery to Grade $\leq$ 1 or baseline; may restart at 1 dose level lower (ie, Phase 1: 280 mg/day for 560 mg/day cohort; or 560 mg/day for 840 mg/day cohort or Phase 2b: reduce daily dose by 2 capsules/day)
Fourth	Discontinue study drug*

\*If study drug is discontinued for toxicity, subject will end the Treatment Phase of the study.

Changes must be recorded in the Dosage Administration section of the case report form (CRF).

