**Table 3: Intrasubject Dose De-escalation by Assigned Daily Dose**

Assigned Daily Dose	420 mg (3 x 140 mg)	560 mg (4 x 140 mg)	840 mg (6 x 140 mg)
Dose De-escalation Level 1	280 mg (2 x 140 mg)	420 mg (3 x 140 mg)	700 mg (5 x 140 mg)
Dose De-escalation Level 2	140 mg (1 x 140 mg)	280 mg (2 x 140 mg)	560 mg (4 x 140 mg)

If complete resolution or improvement of the toxicity to Grade 1 or to baseline values is achieved within 28 days, the investigator may elect to have the subject restart treatment with study drug. If the toxicity takes more than 28 days to resolve, then discussion with the medical monitor is required prior to the subject restarting treatment with study drug. Upon restarting treatment with study drug, the investigator may elect to reduce the subject's dose of study drug by 1 dose level, or by 2 dose levels if previously dose reduced, if the toxicity is considered likely related to study drug and likely to recur at the subject's current daily dose. Otherwise, study drug should be restarted at their current daily dose.

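### Protocol Section 6.5.1 gives two restart rules with no stated precedence: they can differ by one dose level at a second or third occurrence, and only one addresses a fourth

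*Protocol*

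**What the plan says.** Both rules are in protocol Section 6.5.1.

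Table 2 ties the action for non-hematologic events to the occurrence:

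- First: "may restart at original dose level".
- Second: "may restart at 1 dose level lower (ie, Phase 1: 420 mg/day for 560 mg /day cohort", with a matching example for the 840 mg cohort.
- Third: "may restart at 1 dose level lower (ie, Phase 1: 280 mg/day for 560 mg/day cohort", again with an 840 mg example, and the alternative "or Phase 2b: reduce daily dose by 2 capsules/day".
- Fourth: "Discontinue study drug".

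For hematologic events, Table 2 gives recovery thresholds. The platelet entry ends "no evidence of clinically significant bleeding, follow dose modification guidelines below after first occurrence", and the neutrophil entry refers to the same guidelines.

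Table 3 lists two de-escalation levels for each assigned dose (420, 560 and 840 mg). The paragraph beneath it has no occurrence count. Once the subject has recovered, the investigator may choose to reduce "by 1 dose level, or by 2 dose levels if previously dose reduced". The condition is that the event is thought probably due to the drug and apt to return at the present dose. If that condition is not met, "Otherwise, study drug should be restarted at their current daily dose".

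Section 4.1 describes a single Phase 2 study with two Simon stages and Cohorts 1 to 4.

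**The concern.** Two texts in one section answer the same question (at what dose does a subject restart?) by different logic. One counts events. The other asks for a judgement about relatedness and recurrence. Nothing says that either prevails. The hematologic entries send the reader to guidelines below, which could mean the occurrence rows or Table 3 with its paragraph.

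Sections 2.4.3.1 (atrial fibrillation), 2.4.3.4 (diarrhea) and 2.4.3.6 (interstitial lung disease) all direct investigators to Section 6.5.1. Two sites could meet the same repeat toxicity, each follow the protocol, and restart at different doses. This is first a patient-safety instruction.

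There is also a reporting consequence. SAP Section 8.6 cites protocol Section 6.5 as the source of hold and reduction criteria and summarizes dose reductions. SAP Section 5.8 defines relative dose intensity, and SAP Table 7 tabulates adverse events leading to reduction or discontinuation. These summaries would partly reflect which text a site followed.

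The phase labels in Table 2 add a separate difficulty: a reader of this protocol cannot tell which label applies to which cohort.

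**Working it through.** No sample size, power or error rate is involved. The check sets the two texts side by side and does the capsule arithmetic.

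**Inputs.** Capsule strength is 140 mg (Section 6.2). Assigned doses are 420, 560 and 840 mg/day, that is 3, 4 and 6 capsules (Section 6.3.1).

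**Dose ladder.** Level 1 = assigned − 140; Level 2 = assigned − 280.

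- 420: 280 and 140
- 560: 420 and 280
- 840: 700 and 560

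All six values reproduce Table 3. They also reproduce the mg examples in Table 2 for 560 and 840 mg, and Table 2's rule of removing one or two capsules gives the same levels for every cohort. The levels are therefore consistent, and any conflict lies in the rule for moving between them.

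**Restart dose in mg/day, for assigned 420 / 560 / 840:**

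| Occurrence | Table 2 | Paragraph, reduction elected | Paragraph, otherwise clause |
|---|---|---|---|
| First | 420 / 560 / 840 | 280 / 420 / 700 | 420 / 560 / 840 |
| Second, no earlier reduction | 280 / 420 / 700 | 280 / 420 / 700 | 420 / 560 / 840 |
| Third, after one reduction | 140 / 280 / 560 | 140 / 280 / 560 counting from assigned; 0 / 140 / 420 counting from current | 280 / 420 / 700 |
| Fourth | Discontinue | No count, no limit | No count, no limit |

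**Second occurrence.** If reduction is elected the difference is zero. Under the otherwise clause it is 420 − 280 = 560 − 420 = 840 − 700 = 140 mg/day, one level. This path is reachable: the hold criteria include persistent Grade 3 or 4 nausea, vomiting or diarrhea with no requirement that it be drug-related. An investigator can therefore hold for such an event and then judge it unrelated or unlikely to return.

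**Third occurrence, subject already at Level 1.** If reduction is elected and the two levels are counted from the assigned dose, the difference is zero. Under the otherwise clause it is 280 − 140 = 420 − 280 = 700 − 560 = 140 mg/day, one level. Counting two levels from the current dose gives 280 − 280 = 0, 420 − 280 = 140 and 700 − 280 = 420. None of these is a Table 3 level for that assigned dose. The paragraph does not say which count is meant.

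**Fourth occurrence.** Table 2 ends treatment. The paragraph contains neither a count nor a stopping step. The mandatory-withdrawal list in Section 6.6 has no fourth-occurrence item, so it does not settle the matter.

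**Labels.** Elsewhere in the protocol Phase 1 refers to other studies (for example Sections 2.5 and 6.8.3), and Phase 2b appears only in Table 2.

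**The case against.** The strongest reply is that the texts can mostly be read together.

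- *Third occurrence.* A reader might infer that the paragraph allows a two-level cut where Table 2 allows one. The documents do not support that. Table 2's third-row examples are two capsules below the assigned dose and equal Level 2 of Table 3, so its wording means one step below a dose already reduced. Counting from the assigned dose, which the title of Table 3 suggests, the paragraph reaches the same place. This objection stands, except that the paragraph leaves the reference dose unstated.
- *Fourth occurrence.* A reader might infer that the paragraph tells sites to continue. It does not. It covers the dose once treatment restarts and is silent on a limit, so it can be read as operating within Table 2's stopping step. Section 6.6 also requires withdrawal for an adverse event that prevents further dosing. This stands as a description: the gap is silence, not an opposing order.
- *Cohort 1 and the labels.* The 420 mg dose has no mg example in Table 2, but Table 3 and the capsule rule both supply its levels. Either phase label leads to the same ladder. Both points stand.
- *Permissive wording.* Table 2 says *may* in its first three rows. This makes the first occurrence compatible. It does not resolve the second, because the paragraph's otherwise clause says *should* and names a different dose from the one Table 2 permits.
- *Analysis.* The exposure summaries are descriptive, relative dose intensity uses the assigned dose as its denominator, and SAP Section 8.8 plans no inferential comparison between cohorts. This stands, and it limits the statistical consequence.

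**Conclusion.** The conflict is real but narrow. At a second or third occurrence the two texts can differ by one dose level, 140 mg/day, when the paragraph's otherwise clause applies. They coincide when the investigator elects reduction and levels are counted from the assigned dose. It would go too far to infer that they always differ by at least one level. At the fourth occurrence one text stops treatment and the other sets no limit. Neither is given precedence. The phase labels are a drafting error with no dose consequence shown.

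The size rests on two assumptions: the subject is at the same current dose under either text, and at a third occurrence has been reduced once. The documents do not say how often the otherwise clause would apply, so no frequency can be given.

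The reason to act is that sites could follow a safety instruction in different ways. A reader might also infer a threat to the trial's main result. The documents give no basis for that: the primary analysis, sample size and error rates are unaffected.

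**What to change.** Reconcile Table 2 with the paragraph under Table 3, so that each occurrence leads to one stated action for each assigned dose:

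- State which text governs at each occurrence, including the fourth.
- State whether dose levels are counted from the assigned or the current dose.
- Replace the Phase 1 and Phase 2b labels with this study's cohorts.

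Which rule is right is a clinical decision for the sponsor, and this review does not propose one.

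The cost is protocol wording and a clarification to sites. No analysis, sample size or decision threshold changes.
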